2.2 Study Rationale

Rationale for duration of interventions and follow-up, and masking procedures: 1) The proposed study uses some elements of the design used in our R21 pilot with novel features of not using psychotropic drugs, double-blind assignment and masking procedures to treatment groups, and the 2 active control conditions to assess the effects of the interventions on the improvement in primary and secondary clinical outcomes, and biomarkers. Based on our pilot study, participants needed 12 weeks to learn and master TCC and thus a 12-week duration is necessary for the active treatment trial.

The post-intervention follow-ups *will include all participants including those who could show worsening of symptoms and discontinue the study* to follow and compare the effect of TCC versus HEW to explore the role of biomarkers as predictors and moderators of the response. Those who agree to follow-up and do not demonstrate response or show worsening will be encouraged to seek treatment alternatives that will be documented in the chart and controlled for in analyses (e.g. types of treatments, dose, and duration). Most participants will be treated in UCLA clinics and their treatment records will be available for review of response patterns. *Follow-up of 6 and 12 months (or 24 months if 12 months have passed) will allow us to document maintenance of symptoms improvement, relapse of major depressive episodes, and compare the rates of maintained remission between the groups, as well as predictor/moderator effects of the biomarkers.*

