4. SELECTION AND ENROLLMENT OF PARTICIPANTS

SOP: Patients will be assessed at screening and at baseline prior to the initiation of the intervention and biweekly thereafter until 12 weeks, and monthly between 3 and 6 month follow-up. There will also be a final Month 12 follow-up. If unable to schedule this final follow-up, participant will follow-up at Month 24 instead. Those who meet criteria after a telephone screening, will be invited for an in-person screening interview that may be split into 1-3 visits to accommodate clinical, neuropsychological, MRI and laboratory procedures. Baseline assessment (“Baseline 2”) will be performed within 2 months of the start of the interventions. The informed consent form will be reviewed with the participant, and signed prior to initiation of the assessments. Inclusion and exclusion criteria will be reviewed using the inclusion/exclusion

criteria form completed as a source document at screening, baseline, and prior to the first day of TCC and HEW classes.

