6. STUDY PROCEDURES

All study assessments will be conducted in a private examination room at either at UCLA Semel Institute or the UCLA Motion Picture Television Fund Campus.

Screening Procedures (Screening / Visits 1a-c): The informed consent form will be reviewed with the participant during the first in-person visit. There will be general medical and psychiatric history taken, vital signs (blood pressure, pulse) (5 minutes duration), and an ECG (electrocardiogram) will be performed (25 minutes). The questionnaires and screening procedures are performed to determine eligibility. The initial visit will last approximately 2 hours.

Clinical Assessments will be performed in 2-3 visits due to participant's burden: (Tables 1;3). Diagnosis. The Structured Clinical Interview DSM-IVTR-5 (SCID)¹²¹ will be used to make a diagnosis of major depression or other mood disorders or rule out other diagnoses (e.g., psychosis and dementia) at screening. Inter-rater reliability for all instruments will be established at the beginning of the trial across both sites and all staff members on the first 5 recruited patients, it will be rechecked routinely twice a year for consistency throughout the study. Master level research associates supervised by the PI will be trained to reliability for the diagnostic interview (SCID) and other assessments. The current inter-rater correlation coefficient (ICC) for SCID ratings among SCID interviewers is ≥ 0.9 . A second level of reliability check is afforded by a bi-weekly diagnostic consensus conference during which diagnosis is also confirmed.

Blood Samples. During screening procedures between 1st in-person visit and visit 2, blood will be drawn by needlestick for routine laboratory testing and genetic analysis (15 minutes). The blood samples will be processed at the UCLA Clinical and Translational Research Center (CTRC). Approximately 8 tablespoons of blood will be drawn. This visit can be combined with either the visits for MRI or Cognitive testing visit.

Screening diagnostic / Neuropsychological Evaluation Visit (Visit 2):

[name] or a designated member from the study staff will conduct a neuropsychiatric evaluation using cognitive assessments during Visit 2 that takes about 2-3 hours.

Visit 3. Magnetic Resonance Imaging (MRI) Scan. One MRI brain scan will be performed. The scan will occur at the UCLA Brain Mapping Center. MRI Safety metal screening will be performed. Only 55 pts/arm will undergo the fMRI procedure.

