Visit 4. Baseline visit will be performed within 2 months prior to initiation of the interventions with assessment of mood and vital signs (30 min)

Follow-Up Visits (Visits 4-9 and 12-13): Follow-up assessment will occur bi-weekly (every 2 weeks) for 12 weeks and then monthly in order to ensure safety. Each visit will last approximately 30 minutes. Interviews and questionnaires will be used to determine if the treatment is working and useful. Adherence will be monitored at each visit. At each follow-up visit, vital signs will be measured (5 minutes), practice and homework log will be reviewed, and questionnaires will be administered (25 minutes).

Weekly Tai Chi or Health and Wellness Education (12 classes): Weekly Tai Chi or health and wellness education training will occur every week for 60 minutes for 12 weeks. The weekly sessions will last approximately 60 minutes per class. Homework adherence and diaries will be monitored at each class.

Visits 10/11 and 14-19- Outcomes and Endpoints. 12 week follow-up visit (Visit 10/11): During the final visit, a physical, psychiatric examination, and a follow-up blood draw for genetic analysis will be repeated. MRI will be repeated at 12 weeks. The follow-up visit 12 will be split in 2 visits (for clinical, cognitive, laboratory, and MRI) will last 4 hours (1 hour MRI). The 6-month follow-up

visit (14/15) will be approximately 1.5 hours. Both the 12- or 24-month follow-up visit will be split in 2 visits (for clinical, cognitive, laboratory, and MRI) will last 4 hours (1 hour MRI). The Month 12/24 visit will be completed by only those participating in the MRI portion of the study. Since this visit was added onto the original study, some of the participants may have passed their Month 12/24 time point. We will allow this visit to occur any time succeeding the Month 12 mark, and will note the visit type by proximity of their timeline (ie: Participant completes visit at Month 17, would be assigned to Month 12 Visit).

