MRI Imaging Biomarkers: Imaging data will be acquired from 110 subjects (55 per group) at baseline, at 12-weeks post-randomization (or for early termination), and at 12-months post-randomization on a Siemens Prisma system using a 32-channel head coil. Each scanning session will last 60 minutes and include 1) a T1-weighted multi-echo MPRAGE (MEMPR) sequence with real time motion tracking and correction for the examination of brain structure; 2) a bandwidth matched T2-space sequence for detection and quantification of WMHs and CSF; and 3) three separate BOLD EPI sequences for the acquisition of rs- and task-related fMRI data used for the examination of emotional and working memory processing and functional connectivity. In addition, a 3-plane localizer and a non-BOLD EPI sequence co-planar to the fMRI data for cross-modal image registration will be acquired. The morphometry sequences are optimized for determining brain tissue contrast with reduced distortion.¹¹³

Table 5. fMRI sequences

3D T1 MEMPAGE	TEs/TR= 1.74, 3.6, 5.46, 7.32/2530 ms, TI=1260 ms, FA=7, FOV=256 mm, matrix=256x192, voxel size=1 mm ³ , run time: 8:14 min.
3D T2 SPACE	TE/TR= 425/3200 ms, FA='T2 var', FOV=256 mm, matrix=256x192, voxel size=1 mm ³ , ETL=769, 2xGRAPPA, run time: 4:43 min.
fMRI (emotion and working memory)	TE/TR=25/2500 ms, FA=80°, matrix 64x64, FOV=20 cm, 34 axial slices, slice thickness 3 mm, .75-mm gap, run time: ~6 min each.
Resting state fMRI	TE/TR=30/2000 ms, FA=80°, matrix 64x64, FOV=20 cm, 34 axial slices, slice thickness 3 mm, .75-mm gap, run time: 8 min.

Functional Imaging: To address our hypotheses that TCC versus HEW will result in greater activation in right VLPFC and the amygdala during emotional processing (Hypothesis 2a) and greater working memory-related activation in the DLPFC and other network regions (Hypothesis 2b) we will employ two widely-validated brain activation tasks that probe emotional processing and working memory function (see preliminary studies). Similarly, analysis of rs-fMRI data will

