6.2.4 Follow-up Visits

Follow-up Assessments: Assessments of efficacy and safety will take place approximately every 2 weeks for the remaining weeks of the 12 week trial, followed by naturalistic monthly follow-up from **4-6 months**. All follow-up visits, except those at 3, 6, and 12 months- will last for about 30 min. Due to the nature of our population of older adults who may forget their appointments or have competing medical appointments some flexibility in scheduling will be allowed with the interval (+/-) 1 full week of the expected week throughout the study.

Similarly, longer assessments at months 3, 6, and 12 may be split into to 2 visits to accommodate clinical, neuropsychological, MRI and laboratory assessment (at 3 and 12 months). The MADRS, HAM-D, and GDS are to be obtained once between the baseline and screening visits, but re-administered at baseline if the baseline visit occurred significantly after the screening visit for 2 months or later. If participant is unable to complete at Month 12, this follow-up will be completed at Month 24.

We will assess home practice and adherence, safety and medications at each assessment visit. The visit frequency will serve as an additional safeguard to monitor worsening of depression, and the emergence of side-effects or suicidal ideations. All behavioral outcome assessments will be identical in both groups and performed by the trained raters blind to the treatment assignment (*Table 2*).

6.2.5 Completion/Final Evaluation (will be scheduled within a window of +/- 1 week in regards to the week of the final class)

The follow-up visits at 3, 6, and 12 months will last 1.5-3 hours for outcome measures.

Visit 10-11 at week 12: A physical, psychiatric examination, and a follow-up blood draw and MRI for peripheral biomarker analysis will be repeated.

Visit 14-17 at 6 and 12 months - will reassess primary and secondary outcomes and the remission/relapse status.

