9.2 Sample Size and Randomization

Power and sample size estimate: We assume that dropout will be at 10% and 20% at the end of 12 week treatment phase and 6 and 12 month follow-up, respectively. For Aim 1, if the treatment main effects are linear over the 12 week treatment phase on HAMD, our design with 7 time points (baseline, 2, 4, 6, 8, 10, 12 weeks) and with complete data on 99 subjects within each arm (10% dropout) will have 80% power at significance level $\alpha=0.05$ for detecting a treatment and time interaction corresponding to no difference at baseline and a difference of $d = 0.32$ SDs between any two arm at the end follow-up. Our R21 project found an effect size of 0.65 in HAMD between TCC and HEW at 12 weeks. If treatment effects continue to grow linearly over the 6 and

12 month follow-up, our design with complete data on 88 subjects within each arm (20% dropout) will have 80% power at significance level $\alpha=0.05$ for detecting a group difference between any two arms of $d = 0.36$ SDs at 6 and 12 month follow-up. The reported power is based on number of subjects with complete data, and hence is a conservative estimate of the actual power of our design, since the proposed GLMM framework utilizes all observed data collected from all subjects. In addition, the reported power analysis is based on a correlation of 0.5 between measurements obtained at different time points. Selection of the covariance structures within the GLMM model will be based on likelihood ratio test and/or AIC (Akaike Information Criterion). If we find either significant interactions or main effects, follow-up contrasts will be used to determine at which time points there has been significant change and/or differences in treatment effects relative to baseline.

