For Aim 2 of detecting group differences in imaging biomarkers, our design with complete data on 55 subjects within each arm at the end of treatment will have 80% power at significance level $\alpha=0.05$ for detecting a group difference between any two arms of $d = 0.53$ SDs. Our preliminary studies reported in Section 1.1.2 for antidepressant treatment response, found effect sizes of $d = 0.57$ for changes in BOLD response in bilateral occipital cortex and right VLPFC (faces affective reactivity task), in BOLD response in left DLPFC, premotor and bilateral posterior parietal regions (N-Back task) between baseline and end of treatment at 16 weeks. If TCC changes in brain function resemble those induced by psychopharmacological agents, our design will have enough power to detect group differences in imaging biomarkers.

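### Section 6 limits the Month 12/24 visit to MRI participants (55 per arm), but section 9.2 computes month-12 power on 88 per arm

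*Combined protocol and SAP*

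**What the plan says.** **MRI only.** In the outcomes and endpoints text of section 6, "The Month 12/24 visit will be completed by only those participating in the MRI portion of the study". The sentence before it describes the 12- or 24-month visit as covering clinical, cognitive, laboratory and MRI work, so the limit as written removes the HAMD as well as the scan. Section 6 adds that "Only 55 pts/arm will undergo the fMRI procedure", and section 6.2.1 agrees: "Imaging data will be acquired from 110 subjects (55 per group) at baseline".

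**No MRI condition.** Section 2.2 says that the post-intervention follow-ups "will include all participants including those who could show worsening of symptoms and discontinue the study". Section 4 says "There will also be a final Month 12 follow-up". Section 6.2.5 says "The follow-up visits at 3, 6, and 12 months will last 1.5-3 hours for outcome measures" and has relapse documented in person at months 6 and 12. Section 8 invites subjects who do not improve, worsen or relapse back at months 6 and 12. Section 9.5 has every outcome measure given at 12 months. The Appendix A schedule lists HAMD at Month 12 (or 24) without restriction.

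**Power.** Section 9.2 says that "complete data on 88 subjects within each arm (20% dropout) will have 80% power" for d = 0.36 at months 6 and 12, with correlation 0.5 between visits and an effect that keeps growing linearly. Its dropout figures are 10% at 12 weeks and 20% at follow-up. The Sample Size and Population text and section 4.3 instead call the 20% additional to the first 10%, although the former still prints 88.

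**Timing.** Section 6 allows the last visit at any point after month 12 and labels it by the nearest nominal time. Its own example assigns a Month 17 visit to Month 12.

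**The concern.** A visit limited to 55 per arm cannot supply 88 complete subjects per arm. Month 12 is named in Hypothesis 1, and maintenance of effect is a planned secondary mixed-model analysis in section 9.6. If the MRI limit governs, at least half of each arm (55 of 110) has no month-12 HAMD by design, against the 20% loss assumed. A null maintenance result would then be read against a power figure that does not apply.

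Section 9.6 places its dropout comparisons and pattern-mixture analysis under the 12-week primary analysis. If they are extended to follow-up, subjects who were never due to attend could be counted as dropouts. The loose visit label also lets one nominal time point cover different lengths of follow-up.

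**Working it through.** **Inputs.** From section 9.2: d = 0.36, alpha 0.05, correlation 0.5, linear growth, 88 per arm. From sections 6 and 6.2.1: 55 MRI subjects per arm. Assumed, because the plan does not say: two-sided test, compound symmetry, common baseline mean, visits at 0, 6 and 12 months, last visit at exactly month 12.

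**Formula.** Let z be visit time divided by 12 months and m the number of visits a subject has. With correlation 0.5, n subjects per arm contribute n × q, where q = 2[Σz² − (Σz)²/(m + 1)]. Then SE = √(2/Σnq), power = Φ(0.36/SE − 1.96), and the d detectable with 80% power is 2.80 × SE.

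- Visits 0/6/12: q = 2[1.25 − 2.25/4] = 1.375
- Visits 0/6 only: q = 2[0.25 − 0.25/3] = 0.333

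**Counts per arm.** 110 × 0.8 = 88. Additional 20%: 110 × 0.9 × 0.8 = 79.2, or 110 × 0.7 = 77. MRI group with 20% loss (an assumption): 55 × 0.8 = 44.

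| Data per arm | Σnq | SE | Detectable d | Power at 0.36 |
|---|---|---|---|---|
| 88 complete (the plan) | 121.0 | 0.129 | 0.360 | 80.0% |
| 55 MRI only | 75.6 | 0.163 | 0.456 | 60.0% |
| 55 MRI + 33 others to month 6 | 86.6 | 0.152 | 0.426 | 65.9% |
| 44 MRI only | 60.5 | 0.182 | 0.509 | 50.8% |
| 44 MRI + 44 others to month 6 | 75.2 | 0.163 | 0.457 | 59.8% |
| 79.2 complete | 108.9 | 0.136 | 0.380 | 75.7% |
| 77 complete | 105.9 | 0.137 | 0.385 | 74.5% |

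The first row reproduces the plan's figure. The same formula with visits at 0, 3 and 6 months and z scaled to month 6 also gives 0.360 for 88 per arm, so the month-6 claim is not in dispute.

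**Adding month 3.** q becomes 1.400 for 0/3/6/12 and 0.344 for 0/3/6. For 55 + 33, Σnq = 77.0 + 11.3 = 88.3 and power is 66.7%. For 88 complete, Σnq = 123.2 and power is 80.7%.

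**Other models, 55 + 33 against 88 complete:**

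- Effect strictly linear over all 11 scheduled HAMD visits: 75 to 79% against 86 to 89%. With 44 + 44 it is 69 to 74%.
- Month-12 effect left free, time as categories: 60.5 to about 63% against 78.7%. The 55 alone give 58.7%.
- Half of attendees seen at month 17, with linear growth assumed to continue past month 12: 80.4% against 92.5%. Section 9.2 does not assert growth beyond month 12.

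**The case against.** The strongest objection is that the reproducing model is inferred. Section 9.2 does not list its follow-up visits or say how baseline is handled. The 12-week figure needs a different model: with the group term free and 7 equally spaced visits, q = 2 × 28/36 = 1.556, SE = √(2/(99 × 1.556)) = 0.114 and d = 0.319, matching the stated 0.32. Freeing the group term at 0/6/12 months gives q = 1.0 and only 66.6% power for 88 per arm. The follow-up model was therefore chosen because it fits. Section 9.6 also plans one model on all time points, and a strictly linear effect over 11 visits leaves 55 + 33 close to 80%. This stands as a limit on the exact percentage. It does not rescue the stated figure, because every alternative shows a loss of roughly 8 to 18 points against 88 complete subjects in the same model.

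A second objection is that a specific rule can qualify general wording: most of the other sections do not mention MRI status, and section 2.2 is mainly about keeping subjects who worsen or discontinue. That is fair for several of them. It does not remove the conflict between 55 attendees and 88 complete subjects, nor the statement in section 9.5 that all outcome measures are given at 12 months.

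Finally, month 12 is a secondary analysis, and nothing says the visit label will serve as analysis time. Both are correct. They limit the severity, and the timing point is a request to specify.

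**Conclusion.** The point holds and should be fixed. The documents give two incompatible attendance rules for Month 12/24, and the month-12 power statement is compatible with only one of them.

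If the MRI limit governs, power at d = 0.36 is about 60 to 67% rather than 80%, and the detectable d is about 0.42 to 0.46 rather than 0.36. These figures rest on the inferred common-baseline linear model, on visits at exactly month 12, and on no loss among the 55. With 20% loss in that group, the 0/6/12 model gives about 51 to 60%. If the unrestricted sections govern, the attendance conflict does not touch the 80%.

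Under either rule, the additional-20% wording disagrees with the printed 88; taken literally it gives 77 to 79 per arm and about 75 to 76% power. The attendance conflict does not affect the week-12 primary analysis or month 6.

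**What to change.** Reconcile section 6 with sections 2.2, 4, 6.2.5, 8, 9.5, the sample-size text and Appendix A on who attends Month 12/24. Which rule holds is for the sponsor to decide.

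If the MRI limit stands:

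1. In section 9.2, give month-12 n, detectable d and power separately from month 6, with the loss assumed inside the MRI group and the visits and model used.
2. Keep the single all-subject mixed model of section 9.6 and add imaging stratum, already a randomisation stratum in section 6.2.2, as a covariate.
3. Code month-12 absence of non-MRI subjects as planned, so that no follow-up missing-data analysis counts it as dropout.

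In either case:

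4. Make the dropout wording in the sample-size text and section 4.3 agree with the 88 and with section 9.2.
5. Use actual months since randomisation for the Month 12/24 visit in the follow-up model.

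The cost is less favourable stated month-12 figures if the limit stands, and minor analysis wording. Keeping the limit needs no extra patients or visits. If the unrestricted sections govern and sites have been following section 6, non-MRI subjects would have month-12 visits still to be made.

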6.1 Schedule of Evaluations

Assessment schedule.

6.2 Description of Evaluations

Primary outcome measures will include efficacy evaluations using the 24-item HAMD¹¹⁰ to quantify mood symptoms. **Secondary outcome measures** will include the Clinical Global Impression-Severity and Improvement scale (CGI)¹²² to quantify overall severity and clinical improvement over time (2 min). In addition, we will administer the Montgomery Asberg Depression Rating Scale (MADRS)- commonly administered in geriatric depression that is easily comparable to other trials, and the Geriatric Depression Scale (GDS),¹²³ a self-assessment scale often used in geriatric depression trials (10 min).

Measures of comorbid neuropsychiatric symptoms will include the Hamilton Anxiety Scale,¹¹³ a widely used measure of anxiety symptoms (10 min), the Apathy Evaluation Scale (AES),¹¹¹ a measure of the severity of apathy (15 min), and the Unified Parkinson's Disease Rating Scale (UPDRS)¹²⁴ used for the assessment of psychomotor slowing and extrapyramidal symptoms (10 min). Pittsburgh Sleep Quality Index (PSQI) is an 18 item self-report measure of subjective sleep quality (5 min).¹²⁵

Measures of medical comorbidity will include the Stroke Risk Factor Prediction Chart (SRF)^{126,127} of the American Heart Association for rating cerebrovascular risk factors (5 min) and the Cumulative Illness Rating Scale-Geriatric (CIRS-G)¹²⁸ used for rating the severity of chronic medical illness in 14 organ-systems (15 min). *Health-Related quality of life and physical functioning* will be determined using the Medical Outcomes Study Short Form 36-Item Health Survey (SF-36),¹²⁹ that records health-related quality-of-life, mental, physical, and social functioning (15 min), the Connor-Davidson Resilience scale (CD-RISC), as a measure of stress coping ability¹³⁰(5 min), the Quality of Life Enjoyment Scale (Q-LESS-Q),¹³¹ a brief assessment instrument of life satisfaction commonly used in clinical trials of psychiatric populations including the elderly (5 min). Pain assessment has been also included as a measure of self-rated pain to monitor any changes in the pain severity over time (5 min) We will also include a self-reported physical activity record for monitoring physical activity in both groups (3 min).¹³²

Neuropsychological Assessments: Neuropsychological tests will be administered **at baseline, week 12, and at 6, and 12 or 24 months**. Our approach to cognitive assessment and analyses is based on our prior work and benefits from the neuropsychological expertise of [name] who will train research staff on cognitive assessment. We will use a focused test battery developed by [name] sensitive to assessing domains shown as impaired in geriatric depression through prior research by our group and others.^{25,133-135} Domains of cognition will be assessed which are likely to show impairment in geriatric depression (1) Executive functioning, which will be separated into the two areas of primary interest—cognitive set-shifting and inhibitory control; (2) working memory; (3) information processing speed and attention, including an indices of complex and

sustained attention); (4) episodic memory/delayed recall. Most of the measures have 2 or 4 alternate forms so that unique forms may be administered to subjects during repeat testing. In addition to the cognitive outcome measures, we will include a brief word reading test, the Wechsler Test of Adult Reading (WTAR),¹³⁶ to estimate premorbid cognitive functioning. We will conduct a confirmatory factor analysis to assess the goodness of fit of our *a priori* domain assignments. Cognitive domain scores will be obtained as follows: for each cognitive test, raw scores will be converted to standardized (Z) scores with a mean of 0 and a SD of 1, combining all subjects. For each of the tests in a domain, the Z scores will be averaged to create a single Z score. The primary focus will be on executive functioning and working memory

Neuropsychological assessment by specific composite domain.

COMPOSITE DOMAIN	NEUROPSYCHOLOGICAL TESTS AND VARIABLES DERIVED FROM EACH
Language	Boston Naming Test (total correct); Category Fluency (total animals named in 60 seconds); Letter Fluency (total words generated for F, A, and S in 60 seconds each)
Executive Function	Trailmaking B: Trailmaking A ratio; Stroop Color-Word Interference Test Part C (Kaplan version; seconds to complete)
Attention and Processing Speed	Trailmaking A (seconds to complete); WAIS-IV Digit Symbol Substitution Test Stroop Color Naming and Word Reading (average of seconds to complete)
Visuospatial Ability	WAIS-IV Block Design; Rey-Osterreith Complex Figure (total score for copy using Taylor's criteria)
Episodic Memory	California Verbal Learning Test II (trial 5 vs. Long Delay Free Recall); Rey-Osterreith Complex Figure (total score 30-minute delayed recall)

